6.3 Toxicities and Adverse Events

6.3.1 Toxicities

6.3.1.1 All patients will be seen weekly by their treating radiation oncologist or coinvestigators (pediatric oncologist) while undergoing therapy. The following toxicities are expected and listed according to their likelihood and whether they are immediate or long term.

Evaluation of toxicity. All participants will be evaluable for toxicity from the time of their first treatment. Evaluation will be by the radiation oncology physician or by the patient's pediatric oncologist by physical examination and testing as indicated in the study calendar. Patients will be seen by the radiation oncologist for each treatment to assess toxicities and adverse events.

6.3.1.2 Immediate Toxicities

Common (>20%)

• Tiredness

- Hair loss in the treatment field
- Skin redness in the treatment field

Uncommon (10-20%)

• Inflammation of the lung

Rare (<10%)

• Nausea

6.3.1.3 Late Toxicities

Common (>20%)

• Scarring of the lung not requiring treatment (permanent)

Uncommon (10-20%)

- Shortness of breath (permanent)
- Skin dryness in the treatment field (permanent)
- Inflammation of the heart (duration weeks)
- Chest wall pain

Rare (<10%)

- Inflammation of the muscles of the chest wall (duration weeks)
- Scarring of the lung requiring treatment (permanent)
- Rib fracture
- Tumors caused by radiotherapy (lifelong)

Extremely rare (<5%)

- Spinal cord injury (permanent)
- Fatal inflammation of the lung

6.3.1.4 Clinical discretion may be used in managing radiotherapy-related side effects.

6.3.2 Adverse Event Reporting

6.3.2.1 Definitions

6.3.2.1.1 Adverse Event (AE)

An adverse event (AE) is any undesirable sign, symptom or medical condition or experience that develops or worsens in severity after starting the first dose of study treatment or any procedure specified in the protocol, even if the event is not considered to be related to the study.

Abnormal laboratory values or diagnostic test results constitute adverse events only if they induce clinical signs or symptoms or require treatment

or further diagnostic tests.

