6.3.2.1.3 Expectedness

Adverse events

6.3.2.1.3.1 Expected adverse event (toxicities)

Expected adverse events are those that have been previously identified as resulting from administration of stereotactic body radiotherapy. For the purposes of this study, an adverse event is considered expected when it appears in the current adverse event list or is included in the informed consent document as a potential risk.

Please refer to Section 6.3.1 for a listing of expected toxicities.

6.3.2.1.3.2 Unexpected adverse event

For the purposes of this study, an adverse event is considered unexpected when it varies in nature, intensity or frequency from information provided in the current adverse event list or when it is not included in the informed consent document as a potential risk.

6.3.2.1.3.3 Attribution

Attribution is the relationship between an adverse event or serious adverse event and the study treatment. Attribution will be assigned as follows:

☐ Definite – The AE is clearly related to the study treatment.
☐ Probable – The AE is likely related to the study treatment.
\square Possible – The AE may be related to the study treatment.
\square Unlikely - The AE is doubtfully related to the study treatmen
☐ Unrelated – The AE is unrelated to the study treatment

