9. PARTICIPANT ASSESSMENTS

Evaluation of response. All participants included in the study will be assessed for response to treatment, unless the subject received systemic therapy prior to the 6 week assessment.. Response in this study will be defined as disease control in the treated lesion at 6 weeks. We will continue to assess response and consider best overall response as a secondary objective.

Each participant will be assigned one of the following categories: 1) complete response, 2) partial response, 3) stable disease, 4) progressive disease, 5) early death from malignant disease, 6) early death from toxicity, 7) early death because of other cause, or 9) unknown (not assessable, insufficient data). By arbitrary convention, category 9 usually designates the "unknown" status of any type of data in a clinical database.

Disease control at 6 weeks will include complete response (CR), partial response (PR) and stable disease (SD).

Patients will be seen weekly during treatment for physical examination and assessment of acute side effects. They will then be seen at one month from the end of study treatment for physical examination, A CT at will be done at 6 weeks post completion of SBRT and then every three months with physical examination and CT scan of the chest during the first year, followed by every 6 months for the next year and then annually until year 5, as is considered standard of care. (See: Study Calendar)

The lesion or lesions treated will be measured as well as new lesions identified. Pulmonary function tests will be done at 3 months post treatment, then at 9 months.

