11.4 Analysis of Secondary Endpoints

Secondary endpoints include relapse elsewhere in the lung and toxicities, and these analyses will be performed by dose level. The method of Kaplan and Meier will be used to characterize time to relapse elsewhere in the lung. All patients who receive any part of the treatment will be monitored for toxicity, and the percent of patients with various toxicities will be tabulated for each dose level. Assuming a total of 15 patients treated at a dose level, if the true probability of a rare toxicity is 5%, the probability of observing 1 or more rare toxicities is 54%. A 90% confidence interval for any toxicity will be no wider than 46%.

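### The adverse-event definition could keep symptom-free lung scarring seen only on CT out of the toxicity table, although untreated scarring is the only common late toxicity the protocol lists

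*Combined protocol and SAP*

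**What the plan says.** Section 6.3.2.1.1 defines an adverse event in two steps. The opening sentence is broad: "An adverse event (AE) is any undesirable sign, symptom or medical condition or experience that develops or worsens in severity". A second sentence narrows it for test findings: "Abnormal laboratory values or diagnostic test results constitute adverse events only if they induce clinical signs or symptoms or require treatment", with a third trigger at its end, "or further diagnostic tests".

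Section 6.3.1.3 has a single entry under common (>20%) late toxicities: "Scarring of the lung not requiring treatment (permanent"). Section 6.3.2.1.3.1, on expected adverse events, points back to that list: "Please refer to Section 6.3.1 for a listing of expected toxicities".

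On capture, section 6.3.1.1 evaluates toxicity "by physical examination and testing as indicated in the study calendar", and the study calendar includes serial chest CT. Section 6.3.2.3.3 routes non-serious adverse events to the toxicity case report forms. For the analysis, section 11.4 says that "the percent of patients with various toxicities will be tabulated for each dose level".

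**The concern.** Scarring that needs no treatment fails the treatment trigger by its own description. If it also causes no symptoms and prompts no further test, it fails all three triggers, and the test-result sentence says that it is not an adverse event. The same protocol lists it as the late toxicity to expect most often and refers to that list when it defines expected adverse events. Nothing says which statement governs.

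At stake is the consistency of the safety description. Documenting safety is a secondary objective (section 2.3). If two assessors can code the same scan differently, the scarring percentage at a dose level depends partly on which sentence each followed. The effect is permanent and the patients are aged 21 or younger, so readers will want to be able to interpret that percentage.

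**Working it through.** **1. The plan's own precision figures (section 11.4, n = 15 at a dose level)**

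- Chance of at least one event at a true rate of 5%: 1 − 0.95^15 = 0.537. The plan states 54%. Reproduced.
- Widest exact (Clopper-Pearson) 90% interval over 0 to 15 events: 0.456, at 7 or 8 events. The plan states 46%. Reproduced.

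The point does not turn on these figures. They confirm that 15 is the right denominator for the scale below.

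**2. One case traced through the text**

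Take a patient whose scheduled chest CT shows scarring in the treated field, with no symptoms and no treatment.

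| Step | Section | Literal reading | Alternative reading |
|---|---|---|---|
| Is it an adverse event? | 6.3.2.1.1 | A test result with no symptoms and no treatment does not count, unless it requires a further test | Scarring is a medical condition under the opening sentence, however it was found |
| Is it on the toxicity list? | 6.3.1.3, 6.3.2.1.3.1 | Yes, but an event must already be an adverse event before it can be called expected | Yes, so the protocol treats it as an adverse event |
| Does it reach the toxicity form? | 6.3.2.3.3 | No, because the form receives non-serious adverse events | Yes |
| Is it in the table? | 11.4 | Not if the form is the source | Yes |

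On the third trigger: section 9 already schedules CT at 6 weeks, every three months in the first year, every six months in the second, then annually to year 5. Routine follow-up of a stable scar may therefore need no additional test. This is an inference; the documents do not say whether one would be ordered.

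**3. Scale**

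Inputs: n = 15 (section 11.4). The true scarring rate p is assumed, because section 6.3.1.3 gives only >20%; 20% is the floor of that category, and 30% and 40% show the range. The share s of scarring cases left off the form is also assumed, because the documents do not give it.

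Expected cases = 15p. Chance of at least one = 1 − (1 − p)^15. Expected cases lost = 15ps.

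| p | Expected cases | Chance of ≥1 | Lost if s = 0 | Lost if s = 0.5 | Lost if s = 1 |
|---|---|---|---|---|---|
| 20% | 3.0 | 0.965 | 0 | 1.5 | 3.0 |
| 30% | 4.5 | 0.995 | 0 | 2.25 | 4.5 |
| 40% | 6.0 | >0.999 | 0 | 3.0 | 6.0 |

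The chance column is the chance that scarring occurs, not the chance that it goes unreported.

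**4. The two ends of the range for 3 cases in 15**

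- All recorded: 3/15 = 20%, exact 90% interval 5.7% to 44.0%.
- None recorded: 0/15, upper limit 1 − 0.05^(1/15) = 0.181, so 0 to 18.1%. This worst-case interval lies wholly below the >20% that the protocol expects.

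**The case against.** The strongest reply is that the protocol already treats this item as an adverse event. It is on the 6.3.1 list; the subsection on expected adverse events sends the reader there; permanent scarring fits the broad opening sentence of the definition; toxicity is evaluated by calendar tests that include CT; and section 6.3.2.2 records events however they are detected. Section 11.4 speaks of toxicities in general and is not expressly limited to events that pass the test-result sentence. Most of this stands. It shows that a sensible assessor could record the scarring, and it rules out saying that scarring would be left out. It does not show that every assessor would record it: the limiting sentence is an explicit rule, the other provisions do not override it, and the toxicity form is the only route named for non-serious events.

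It is also fair that untreated is not the same as symptom-free. Scarring that causes symptoms but is not treated counts on any reading, as does scarring that requires further tests.

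A reader might infer three stronger things that the documents do not support:

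- **That the CT reader may note only lesions.** Section 9 says "The lesion or lesions treated will be measured as well as new lesions identified". It does not say that nothing else may be recorded, and it concerns response assessment.
- **That the trial would report scarring as absent.** A count of 0/15 needs every case to be symptom-free, to need no further test and to be excluded by every assessor.
- **That a comparison of 8, 10 and 12 Gy x 3 is lost.** No such comparison is planned, and escalation stops once a level is found effective (sections 2.1 and 11.1), so higher levels may never be treated.

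**Conclusion.** The point holds as a conflict between a stated recording rule and the protocol's own toxicity list. Symptom-free scarring seen only on a scheduled CT could be left off the toxicity form and out of the section 11.4 table, or could be recorded, depending on the assessor. With p assumed at 20%, about 3 of 15 patients at a dose level are in question, and between none and all of them could be lost. The documents do not allow a narrower range.

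The reach is limited to the secondary safety table. The lung-related dose-limiting toxicities in section 6.2 start at grade 3 (pneumonitis, dyspnea) or grade 4, which scarring without symptoms or treatment should not reach. The escalation rule, the phase II decision and the sample size do not change. The correction is nevertheless worth making, because it concerns the late effect that the protocol expects most often and it is cheap.

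**What to change.** Reconcile sections 6.3.1.3, 6.3.2.1.1, 6.3.2.1.3.1, 6.3.2.3.3 and 11.4:

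- In 6.3.2.1.1, add one sentence: the lung toxicities listed in section 6.3.1, when seen on a protocol chest CT, are recorded as adverse events and graded by CTCAE even without symptoms or treatment.
- On the toxicity form, add a line for these findings.
- In 11.4, state that they are tabulated by cohort and dose level, with the number of patients scanned as the denominator.

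The scans are already scheduled, so the cost is a sentence, a form line, a table row and the time to grade the finding. The downside is that more low-grade events will be listed. This is a recording and reporting rule; no dose, treatment or other clinical management rule changes.

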6.3.2.1.2 Serious Adverse Event (SAE)

A serious adverse event (SAE) is any adverse event, occurring at any dose and regardless of causality that:

- Results in death
- Is life-threatening. Life-threatening means that the person was at immediate risk of death from the reaction as it occurred, i.e., it does not include a reaction which hypothetically might have caused death had it occurred in a more severe form.
 - Requires or prolongs inpatient hospitalization (i.e., the event required at least a 24-hour hospitalization or prolonged a hospitalization beyond the expected length of stay). Hospitalization admissions and/or surgical operations scheduled to occur during the study period, but planned prior to study entry are not considered SAEs if the illness or disease existed before the person was enrolled in the trial, provided that it did not deteriorate in an unexpected manner during the trial (e.g., surgery performed earlier than planned).
 - Results in persistent or significant disability/incapacity. Disability
 is defined as a substantial disruption of a person's ability to
 conduct normal life functions.
 - Is an important medical event when, based upon appropriate medical judgment, it may jeopardize the participant and require medical or surgical intervention to prevent one of the outcomes listed above.

Events **not** considered to be serious adverse events are hospitalizations for:

- routine treatment or monitoring of the studied indication, not associated with any deterioration in condition, or for elective procedures
- elective or pre-planned treatment for a pre-existing condition that did not worsen
- emergency outpatient treatment for an event not fulfilling the serious criteria outlined above and not resulting in inpatient admission
- respite care

6.3.2.1.3 Expectedness

Adverse events

6.3.2.1.3.1 Expected adverse event (toxicities)

Expected adverse events are those that have been previously identified as resulting from administration of stereotactic body radiotherapy. For the purposes of this study, an adverse event is considered expected when it appears in the current adverse event list or is included in the informed consent document as a potential risk.

Please refer to Section 6.3.1 for a listing of expected toxicities.

6.3.2.1.3.2 Unexpected adverse event

For the purposes of this study, an adverse event is considered unexpected when it varies in nature, intensity or frequency from information provided in the current adverse event list or when it is not included in the informed consent document as a potential risk.

6.3.2.1.3.3 Attribution

Attribution is the relationship between an adverse event or serious adverse event and the study treatment. Attribution will be assigned as follows:

☐ Definite – The AE is clearly related to the study treatment.
☐ Probable – The AE is likely related to the study treatment.
\square Possible – The AE may be related to the study treatment.
\square Unlikely - The AE is doubtfully related to the study treatmen
☐ Unrelated – The AE is unrelated to the study treatment

6.3.2.2 Procedures for AE and SAE Recording and Reporting

During the study investigators will assess the occurrence of AEs and SAEs at all participant evaluation time points. AEs will be evaluated using the descriptions and grading scales found in the CTEP active version of the NCI TCAE located on the CTEP website at:

http://ctep.cancer.gov/protocolDevelopment/electronic_applications/ctc.htm.

The current version is CTCAE v4.0.

All AEs and SAEs, whether reported by the participant, discovered during questioning, directly observed, or detected by physical examination, laboratory test or other means, will be recorded in the participant's medical record and on the appropriate study specific case report forms.

Monitoring

All adverse events, both serious and non-serious, and deaths that are encountered from initiation of study intervention, throughout the study, and within 6 months of the last study intervention should be followed to their resolution, until the investigator assess them as stable or determines the event to be irreversible, or the participant is lost to follow-up. The presence and resolution of AEs and SAEs (with dates) should be documented on the appropriate case report form and recorded in the participant's medical record to facilitate source data verification.

6.3.2.3 Reporting Requirements

All investigators are required to abide by the reporting requirements set by the DF/HCC. The study must be conducted in compliance with FDA regulations, local safety reporting requirements, and reporting requirements of the principal investigator (PI). The PI will be notified of all AEs and SAEs.

6.3.2.3.1 Reporting to Institutional Review Board (IRB)

SAEs will be reported directly to the DFCI IRB via the DFCI Office for Human Research Studies (OHRS). Copies of all SAE report forms will be sent to the PI:

[name]

Email: [contact]

[contact] [contact]

6.3.2.3.2 Serious Adverse Event Reporting

All serious adverse events that occur after the initial dose of study treatment, during treatment, or within 6 months of the last dose of treatment must be reported to the DF/HCC Overall Principal Investigator and the DFCI IRB. SAEs include events meeting the criteria outlined in Section 6.3, as well as the following:

Note: If the participant is in long term follow up, report the death at the time of continuing review.

Investigators must report each serious adverse event to the PI within 24 hours of learning of the occurrence. In the event that the participating investigator does not become aware of the serious adverse event immediately (e.g., participant sought treatment elsewhere), the participating investigator is to report the event within 24 hours after learning of it and document the time of his or her first awareness of the adverse event.

Within the following 24-48 hours, the participating investigator must provide follow-up information on the SAE. Follow-up information should describe whether the event has resolved or continues, if and how the event was treated, and whether the participant will continue or discontinue study participation.

6.3.2.3.3 Non-Serious Adverse Event Reporting Non-serious adverse events will be reported to the PI on the toxicity case report forms.

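### The protocol gives conflicting periods for collecting toxicity (6 months, 2 years, or every visit to year 5), and the Section 11.4 toxicity table has no time window, so late toxicity may be under-recorded

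*Combined protocol and SAP*

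**What the plan says.** Several places in the protocol bear on how long toxicity is collected.

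- **Assessment (Section 6.3.2.2).** "During the study investigators will assess the occurrence of AEs and SAEs at all participant evaluation time points". The same section sends all such events to the medical record and the case report forms, and sets no end date for doing so.
- **Follow-up of events (Section 6.3.2.2).** Events met from the start of the intervention, over the whole study, and "within 6 months of the last study intervention should be followed to their resolution", or until they are stable, irreversible or the patient is lost.
- **Serious events (Section 6.3.2.3.2).** Those arising after the first dose, during treatment or "within 6 months of the last dose of treatment must be reported to the DF/HCC Overall Principal Investigator and the DFCI IRB". A note adds: "If the participant is in long term follow up, report the death at the time of continuing review".
- **Non-serious events (Section 6.3.2.3.3).** "Non-serious adverse events will be reported to the PI on the toxicity case report forms". No end date is given.
- **Visits (Section 9).** Examination and chest CT every three months in the first year, "followed by every 6 months for the next year and then annually until year 5".
- **Study Calendar.** The adverse event row is marked for weeks 1 and 2, one month, year 1 and year 2. The column for years 3 to 5 is blank in that row, although history, physical examination and CT are marked there. Footnote b, attached to the row, mentions only serious events up to 6 months after the last dose.
- **Analysis (Section 11.4).** "the percent of patients with various toxicities will be tabulated for each dose level". No time window, early/late split or number under follow-up is specified.

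**The concern.** Section 6.3.1.3 expects harm that lasts or appears late: permanent lung scarring not needing treatment (over 20%), permanent shortness of breath (10 to 20%), and rib fracture and radiation-induced tumors (each under 10%). Patients are aged 21 or younger. Documenting safety is a secondary objective in Section 2.3.

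The dose-limiting toxicity window in Section 6.2 closes 6 months after radiotherapy. A later event therefore cannot count as a dose-limiting toxicity, and the Section 11.4 table is the only planned analysis in which it could appear. Scheduled lung function tests do not fill the gap. They end at 9 months by Section 9 and at 6 months by the calendar footnote, which itself needs reconciling.

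Sites usually work from the calendar. Taken with its footnote, the adverse event row can be read as serious events to 6 months, or as all events to year 2. On neither reading does it call for a toxicity entry in years 3 to 5. The percentages by dose level could then omit late events noticed at visits the trial already holds.

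A second consequence follows from the missing window. Dose levels open one after another within a cohort (Section 11.1), and one renal dose level may take 5 years to accrue (Section 11.2). Crude percentages may therefore compare dose levels with unequal follow-up.

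**Working it through.** **Step 1. Set the periods side by side.**

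| Place | What it governs | Period |
|---|---|---|
| Section 6.3.2.2, assessment and recording | All adverse events | Every evaluation; visits run to year 5 |
| Study Calendar row | Adverse event reporting | Marked through year 2; years 3 to 5 blank |
| Footnote b to that row | Serious events only | 6 months after last dose |
| Section 6.3.2.3.2 | Reporting serious events to the principal investigator and IRB | 6 months after last dose |
| Section 6.2 | Dose-limiting toxicity | 6 months after radiotherapy |
| Section 11.4 | Toxicity percentages by dose level | Not stated |

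The fourth and fifth rows have their own purposes and conflict with nothing. The conflict lies among the first three. The calendar row covers adverse events in general but stops at year 2. Its footnote narrows it to serious events at 6 months. Section 6.3.2.2 has neither limit.

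**Step 2. Reproduce the plan's own figures.** Section 11.4 takes n = 15 patients at a dose level and a true toxicity probability of p = 5%.

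P(at least one) = 1 − (1 − p)^n = 1 − 0.95^15 = 0.537, which matches the stated 54%.

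The widest exact (Clopper-Pearson) 90% interval for n = 15 has width 0.456, reached at 8 events (and, by symmetry, 7). This matches the stated 46%. Neither figure is in error.

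**Step 3. See how the 54% depends on capture.** Let f be the share of patients with the toxicity whose event falls inside the collection window. The documents give no onset times, so f is an assumption and a range is shown. The recorded rate is p × f, and P(at least one recorded) = 1 − (1 − p × f)^15.

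| True rate | f = 1 | f = 0.75 | f = 0.5 | f = 0.25 |
|---|---|---|---|---|
| 5% | 0.54 | 0.44 | 0.32 | 0.17 |
| 10% | 0.79 | 0.69 | 0.54 | 0.32 |
| 20% | 0.96 | 0.91 | 0.79 | 0.54 |

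For example, with p = 5% and f = 0.5 the result is 1 − 0.975^15 = 0.316. With f = 0.2 it is 1 − 0.99^15 = 0.140. The tabulated percentage is expected to be f times the true one, so a 20% toxicity would show as 10% at f = 0.5. If f = 1, nothing is lost.

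**The case against.** The strongest reply is that the protocol already provides for late events. Section 6.3.2.2 has them assessed at every evaluation and recorded on case report forms. Section 6.3.2.3.3 puts no end date on non-serious events, and Section 11.4 has every treated patient monitored for toxicity without a cut-off. Six months is the period for reporting serious events, and the year 3 to 5 visits are described in Section 9 as standard of care. Different periods for different purposes need not clash. The primary endpoints, dose-limiting toxicity to 6 months and response at 6 weeks, are untouched.

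Much of this stands, and it rules out two stronger readings that a reader might infer.

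- *Toxicity capture stops at 6 months.* The documents do not support this. Section 6.3.2.3.2 sets a reporting duty for serious events and still asks for deaths in long-term follow-up. The follow-to-resolution sentence in Section 6.3.2.2 also covers events over the whole study, so it is not a clear 6-month limit.
- *The toxicity table will understate late harm.* This follows only if the 6-month or 2-year limit is applied to data collection. Nor can its size be taken from calendar time: 6 of 60 months (10%) or 24 of 60 (40%) are shares of time, not of events. Eligibility asks only for life expectancy above 3 months, so the number of patients who will reach years 3 to 5 is unknown.

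The reply does not dispose of the calendar. Its adverse event row is blank in a column where other assessments are marked, and that contradicts the general rule in Section 6.3.2.2. The window of the table also remains undefined.

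**Conclusion.** The point holds as an inconsistency with a plausible consequence. Section 6.3.2.2, the Study Calendar and footnote b do not agree on how long toxicity is collected, and Section 11.4 does not say what period its percentages cover. If sites follow the calendar and its footnote, late toxicities that the protocol itself lists may be under-recorded. If they follow Section 6.3.2.2, these would be recorded to year 5.

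The size cannot be derived from the documents. The fall from 54% to 32% rests on the assumption that half of a 5% toxicity lies outside the window, and shows sensitivity only. The stated 54% is correct when the 5% refers to events within the observation window. The matter bears on the secondary safety objective and not on the primary endpoints or their operating characteristics.

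**What to change.** 1. Leave the 6-month window for reporting serious events as it is.
2. In Section 6.3.2.2, state a separate collection period for adverse events, and reword the follow-to-resolution sentence so that its scope is clear.
3. In the Study Calendar, mark recording of treatment-related late toxicity in the year 3 to 5 column. Reword footnote b so that it applies only to serious-event reporting. If the sponsor does not intend to collect toxicity in those years, say so explicitly.
4. In Section 11.4, tabulate early toxicity (up to 6 months, matching the dose-limiting toxicity window) and late toxicity separately by dose level, with the number of patients under follow-up at each period. State that the 54% and 46% figures refer to toxicity within a named window.

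The cost is one additional form at visits already scheduled and slightly more data management. No visit or scan is added. Collection to year 5 will still not cover lifelong risks such as radiation-induced tumors, and the report should say so.
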